Effect of Different Volumes of Training of Pilates Exercises on
Muscle Strength, Postural Balance, Flexibility, Functional Autonomy,
Depressive Symptoms and Pulmonary Function on Elderly

NCT03791502

SEPTEMBER 17, 2019

ABSTRACT

Background: aging is a progressive process that leads to decreased muscle strength and mobility, slowness in reaction time and impaired balance, compromising autonomy and quality of life. **Objective:** to compare the effect of different volumes of Pilates training on strength, balance, flexibility, functional autonomy, depressive symptoms and pulmonary function in the elderly community. **Method:** it will be a randomized clinical trial with elderly of both sexes. The Group A (GA) exercises with smaller volume and greater variability of exercises, Group B (GB) greater volume and lower variability and Group C (CG) will maintain its usual activities. The intervention will occur twice a week for 60 minutes for 12 weeks. In order to evaluate the strength, Biofeedback System for resting exercises with elastic overload (E-lastic®), 30-second chair stand test (30-s CST) and Palmar gripper dynamometer will be used. The balance will be evaluated in the semi-tandem, tandem and unipodal positions, by the Timed Up and Go (TUG) and Step Test. Flexibility will be assessed using the Wells database, functional autonomy, dressing-gown test (VTC), depressive symptoms by the Geriatric Depression Scale (GDS) and lung function by many vacuum and spirometry. Data distribution will be done using the Shapiro-Wilk test, frequency and percentage calculation for categorical variables, the mean and standard deviation for continuous variables with normal, median, and interquartile distribution for variables with non-normal distribution. For comparison of the three groups will be used ANOVA One Way with post hoc of Bonferroni or Kruskal Wallis with Bonferroni correction, comparison of the continuous variables at moments before and after twelve weeks of intervention the Student's t-test paired or Wilcoxon and for the comparison of the categorical variables the test chi-square. **Expected results:** significant improvement of outcomes in both intervention groups compared to CG, however, the group with higher training volume and lower exercise variability will have a greater effect than the group with lower volume and greater variability of exercises. **Keywords:** Exercise Movement Techniques, Elderly, Aging, Muscular Strength, Balance, and Flexibility

Introduction

Aging is an involuntary and progressive process that leads to biological, structural and functional changes such as loss of mass and muscle strength(1,2). The aging process leads to changes in the visual, vestibular, sensory and motor systems, causing slow reaction time, compromising the postural balance (L. (3,4) Flexibility and mobility also tend to decrease with aging favoring the onset of lesions and loss of functional autonomy (5,6). The regular practice of physical exercise helps to prevent these changes related to aging (5).

Among the various possibilities of physical exercise, the Pilates method has been well-suited for the elderly, since it incorporates the training components recommended by the American College of Sports Medicine (ACSM), is the strength, balance, and flexibility (7,8). However, researchers have questioned the lack of scientific evidence that confirms all the benefits of the method, especially in the elderly,(9,10). The findings described in the literature are still controversial. A systematic review of six randomized controlled trials (RCTs) has shown limited evidence in improving strength, flexibility, and balance in both sexes (9).

Physical decline negatively affects the personal autonomy and quality of life of the elderly and Pilates seems to have positive effects on these aspects. Rodrigues et al. (2010)(11) observed a significant evolution in the functional performance of healthy elderly women in rising from the seated position (11.8%) and lying position (26%) and a significant improvement in quality of life ($p = 0.04$) after intervention with Pilates exercises (11). As for depressive symptoms, Mokhtari et al. (2013)(12) identified a significant reduction ($p < 0.007$) in this symptomatology after Pilates practice (12). However, both studies reached only two points on the PEDro Scale. Recent investigations found a significant increase in maximal inspiratory pressure (MIP) of 19.5%, maximal expiratory pressure (MEP) of 8.7% and Abdominal Transversal thickness of 42.3% after the program(13). However, the study presented some limitations, such as the absence of a control group and the inability of the blindness of the evaluators.

It is also important to highlight the lack of reports on how the programs are carried out and when there is a description there is a heterogeneity in the prescription of the exercises. In the two reviews cited above (9,14), only two of

the included studies presented the prescribed volume: ten replicates (11) and three series of ten repetitions (15). Some studies have also described the volume: two sets of ten repetitions (16), two to four sets of 15 to 20 seconds of contraction for isometric exercises and 15 to 20 repetitions for dynamic exercises (17). A single series of 10 replicates with a 30-second interval between the series (18,19). It is known that the literature suggests for the muscular strength gain in the elderly a training volume of two to three sets per exercise, seven to ten repetitions per set and a moderate to high intensity (8,20) and as noted most Pilates exercise programs have not followed these recommendations.

The aim of the study is to compare the effect of different volumes of Pilates exercise training on muscle strength, postural balance, flexibility, functional autonomy, depressive symptoms and lung function in the elderly community. We believe that Pilates exercises will have beneficial effects for the elderly, but our hypothesis is that the group that performs a greater volume of Pilates exercise training will have a greater improvement in the investigated outcomes than the group with the lowest volume.

Methods

Type and location of study

This is a randomized clinical trial, which will be conducted at a Pilates studio in Goiânia.

Participants

The elderly will be invited through advertisements in social networks, local media, and posters distributed in the centers of coexistence of the elderly, health centers and churches and will be selected, considering the possibility of 20 % of sample losses, the first 57 eligible participants according to the following inclusion criteria:

- Age between 60 and 85 years;
- To present cognitive aptitude according to the Mental State Mini-Exam (MMSE);
- Independent walking, without the use of auxiliary walking devices;
- Not participating in other physical intervention research;

- Not having undergone physiotherapeutic treatment and not having participated in a structured physical activity in the previous month;
- Do not present neurological diseases, history of fractures or recent surgeries and serious cardiorespiratory diseases.

Participants will be excluded:

- Failure to attend all stages of evaluation;
- They did not complete 80% of the intervention.

Outcomes and Measuring Instruments

The dependent variables of the present study will be muscle strength, postural balance, flexibility, functional autonomy, depression and pulmonary function.

Muscle Strength

The muscle-dependent variable will be evaluated through the Biofeedback System for The Biofeedback System will be used for the practice of resistance exercises with elastic overload (E-lastic®), The 30-second chair stand test (30-s CST), and the palmar gripper dynamometer

- The Biofeedback System will be used for the practice of resistance exercises with elastic overload (E-lastic®). E-lastic® will measure maximal isometric voluntary contraction of the knee flexor and extensor muscles, flexors, extensors, adductors and hip abductors before and after the intervention. For the acquisition of force signals, a load cell is used to provide an electrical signal proportional to the force that deforms the equipment. The participants will perform 3 repetitions, maintaining the contraction for 5 seconds, with 60 seconds of recovery and the highest value will be recorded.
- The 30-second chair stand test (30-s CST) will be used. It consists of getting up and sitting on a chair as many times as possible within 30 seconds. A seat with backrest and without armrest (with a seat height of 45 cm) is used. Initially, participants remain seated and are instructed to look forward after command "1, 2, 3, will" they raise with their arms crossed on their chest. The evaluator will explain and demonstrate the test and the participant will do once for familiarization. You will be given a rest of 2 minutes to start the test.

- Will be measured using the Saehan® hydraulic palmar gripper dynamometer, the position recommended by the American Society of Hand Therapists (ASHT) will be adopted: sitting comfortably positioned with shoulder lightly bent, elbow bent at 90 °, forearm in neutral position and, finally, the position of the handle may vary from 0 ° to 30 ° of extension. It will be used to record the maximum and average manual grip strength of three measurements and the values will be compared with the reference values.

Postural balance

The static and dynamic body balance will be evaluated.

- Static postural balance: will be evaluated by measuring the time each participant can maintain in three progressively more difficult positions: semi-tandem, tandem and unipodal support. In all positions the individuals must be with their hands on their waist, the total time to stay in each position is 30 seconds and it will have 3 attempts in each position and the best time will be recorded. The evaluator will demonstrate the test once.
- Dynamic postural balance: to evaluate the dynamic balance, the Timed Up and Go (TUG) test and the Step Test will be used. The TUG starts with the participant sitting in the chair, in the "go" command, he gets up from the chair, walks 3 meters at a comfortable pace, turns around, goes back to the chair and sits down. It will be demonstrated once and then it will do a repeat for familiarization. In the Alternative Step Test, the participant is asked to make eight beats of the foot, alternating between right and left, on a step in front of him with a height of 18 cm. Time will be timed and used in the analyzes. The test should be performed in 10 seconds.

Flexibility

To evaluate the flexibility of the hamstring muscles will be used the Sit and Go Test, using the Wells bench, participants will remain without footwear, sitting with knees extended, shoulders flexed, elbows extended and hands overlapped. Participants should perform trunk flexion at the front, perform a forced expiration, and move the seat ladder as far as possible, this procedure will be performed three times and immediately noted by the evaluator, with the best.

Functional Autonomy

The functional autonomy of the upper limbs will be evaluated by the dressing test and a t-shirt. Initially, the evaluator will explain the test and the volunteer will do a brief training with two replicates. The execution time is marked in seconds and the shorter the execution time, the better the result. The subject must make two attempts, where the best performance attempt will be recorded.

Depressive symptoms

The Geriatric Depression Scale will be used for the evaluation of depressive symptoms in the elderly and screening for depression among older people. Geriatric depression scale will be presented as an interview and the questions have a yes / no format to be easy to understand. The short version consists of 15 questions, one point is given for each "yes" answer and the number of points is added to provide a single score. The score ranges from 0 to 15 and a score of zero to five is considered normal, six to ten indicates mild depression and 11 to 15 suggests severe depression.

Respiratory muscle strength

Respiratory muscle strength will be measured by assessing maximal inspiratory pressure (MIP) and maximal expiratory pressure (MEP) in cmH₂O. These measures represent the strength of the inspiratory and expiratory muscles respectively. It will be using the manometer of the brand Globalmed® MVD300, calibrated, the patient seated at 90°, a nasal clip and a nozzle connected to the equipment will be placed. In order to assess MIP, a maximum expiration up to the residual volume and, in the sequence, a maximum sustained forced inspiration will be required. And to assess PEmax inspiration will be required up to the total lung capacity and, subsequently, a forced maximum expiration up to the residual volume. Three reproducible measurements will be made, with variation less than 10% and the values found will be compared with those predicted.

Pulmonary function

Pulmonary function will also be evaluated by spirometry. The test measures forced vital capacity (FVC) in liters (L), forced expiratory volume in the first second (FEV₁) in liters (L) and the FEV₁ / FVC ratio. A One Flow® portable spirometer will be used, the individual will be seated with the head in the neutral position, inspiration will be requested up to the total lung capacity (CPT) and, thereafter, a

maximum expiration, with an explosive start, to the residual volume (lasting at least 6 seconds). A maximum of eight replications will be performed until three reproducible measures (less than 10% difference), 60 seconds of interval between measurements, will be considered the best value. It is recommended to compare the values obtained with predicted equations

Sociodemographic, Clinical, Anthropometric and Feasibility Indicators

To characterize the participants, gender, age, schooling, marital status, concomitant diseases, and life habits will be investigated through a sociodemographic and clinical characterization questionnaire developed by the researchers. A participant who performs at least 150 minutes of moderate physical activity or 75 minutes of vigorous physical activity per week will be considered active (8,21,22). Body mass and height will be measured to calculate the Body Mass Index (BMI). The BMI will be classified according to Lipschitz(23) below 22 Kg / m² will be considered lean, between 22 and 27 kg / m² eutrophy and over 27 kg / m² overweight.

Feasibility indicators will be checked by means of the following items: retention (percentage of withdrawals and withdrawals), adherence to intervention (percentage of Pilates sessions attended and reason for absences), participant experience and feedback (Are the sessions pleasant? Pilates for other people? Did you realize benefits to your health? Would you like to continue with Pilates exercises?), safety (notification of adverse events, be it injury or medical event attributable to Pilates exercise).

Intervention

The intervention will consist of performing Pilates exercises on the apparatus (Reformer, Cadillac, Barrel, and Chair), on the ground and with accessories. It will always be performed by a physiotherapist with teaching certification in the Pilates methodology and will be supervised by two physiotherapist trainees properly trained so that all principles are followed and the exercises performed correctly. Participants will start the exercise program in small groups of up to 8 people, twice a week for 60 minutes, for 12 weeks, totaling 24 sessions.

The first day of intervention for both groups will be devoted to explaining the six principles described by Joseph Pilates: centralization, concentration, control, precision, fluidity, and breathing, and in all sessions these principles will be recalled by the physiotherapist. From the second day of intervention, the participants will follow different exercise programs. Group A (GA) will perform a training with lower volume and greater variability of Pilates exercises and group B (GB) with greater volume and lower variability of Pilates exercises. The control group (CG) will remain with their usual activities. The structure of the exercise program of each group will be detailed below, but both will start performing flexibility exercises, adopting dynamic stretching and then perform the strengthening exercises for the main muscle groups.

- Group A (GA): participants will follow a Pilates exercise program similar to that adopted in clinical practice and to what is described in the literature. The GA prescription will consist of 18 exercises, performed in a single series of seven to 10 repetitions, 60 seconds rest between exercises. Each week the exercises will be changed. The progression will occur increasing the resistance of the springs and the level of difficulty of the exercises, but without modifying the repetitions. The intensity of the training will be measured using the Modified Borg Effort Scale and then kept constant throughout the program in a score of 7. After the end of each exercise, participants will be asked to rate their effort so that the adjustment of the intensity can be carried out properly.
- Group B (GB): participants will conduct a Pilates exercise program based on the ACMS recommendations and the results of the systematic review of Borde, Hortobágyi, and Granacher (2015). The GB prescription will consist of 12 exercises, performed in three sets of seven to ten repetitions, the 60s of rest between sets. Every four weeks the exercises will be changed. The progression will occur increasing the resistance of the springs and the level of difficulty of the exercises. The intensity of the training will be measured by the Borg Scale and then kept constant throughout the program at level 7. After the end of each exercise, participants will be asked to rate their effort so that the intensity adjustment can be performed properly.

Evaluation procedures

Initially, everyone who agrees to participate in the study will sign the informed consent form, then the data concerning the variables: cognitive ability, sociodemographic, clinical characterization, and anthropometric measurements will be collected. All participants will be evaluated for muscle strength, balance, flexibility, functional autonomy, depression and lung function before and after the intervention, including those who do not complete 80% of their presence during the intervention. For the self-report questionnaires an evaluator will be trained and for the performance questionnaires/tests two evaluators will be trained and they will be blind to the intervention. Subjects will be randomized into three groups. The randomization process will be done at random.org and concealment of the allocation will occur using opaque and sealed envelopes.

Statistical analysis plan

A sample size was calculated using the effect size identified in the comparison of the results concerning the post-intervention moment of the intervention and control groups, using data from the literature (18,25,26). The calculation indicated the need for a sample size of 15 participants per group for a power of 80% and an alpha error of 0.05 in the intergroup comparison analyzes for the variables muscle strength, balance, and flexibility.

Initially, the distribution of the data will be determined by means of the Shapiro-Wilk normality test. Subsequently, the descriptive analysis will be performed with frequency and percentage calculation for the categorical, mean and standard deviation data for continuous data with normal distribution and for median and interquartile data for continuous data with non-normal distribution.

For the comparison of the three groups for the performance of the continuous data, the ANOVA One Way test with post hoc of Bonferroni or Kruskal Wallis with Bonferroni correction (according to the normality of the data) will be used. The t-test of paired student or Wilcoxon (according to the normality of the data) will be used to compare the continuous data at the before and after moments in each group. Comparison of categorical data will be done using the chi-square test. For each primary and secondary outcome, the values observed in each group will be described, the size of the estimated effect along with its accuracy (eg, 95% confidence interval). It will be adopted 5% significance level.

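### Safety counts only events attributable to Pilates, so the control group's count is zero by definition and the Pilates groups have no background rate to be read against

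*Combined protocol and SAP*

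**What the plan says.** All references are to the combined protocol and SAP.

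- **Sociodemographic, Clinical, Anthropometric and Feasibility Indicators.** The section introduces four items with "Feasibility indicators will be checked by means of the following items": retention, adherence, participant experience, and safety. The safety item reads "safety (notification of adverse events, be it injury or medical event attributable to Pilates exercise". No other text covers how adverse events are collected, timed, graded, attributed or analysed.
- **Outcomes and Measuring Instruments.** Safety is not an outcome: "The dependent variables of the present study will be muscle strength, postural balance, flexibility, functional autonomy, depression and pulmonary function".
- **Intervention.** The Pilates groups train "twice a week for 60 minutes, for 12 weeks, totaling 24 sessions". On delivery: "It will always be performed by a physiotherapist with teaching certification in the Pilates methodology". For the third arm: "The control group (CG) will remain with their usual activities".
- **Evaluation procedures.** The assessments made in every group are clinical and functional: "All participants will be evaluated for muscle strength, balance, flexibility, functional autonomy, depression and lung function before and after the intervention". Adverse events are not among them. Blinding is stated for the evaluators of the questionnaires and tests: "for the performance questionnaires/tests two evaluators will be trained and they will be blind to the intervention".
- **Participants.** The plan allows for 20% losses, recruits 57 people aged 60 to 85, and excludes those who miss an evaluation stage or do not complete 80% of the intervention.

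**The concern.** The safety item makes causality part of the definition of an event. That has two consequences.

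1. Someone in the control group who falls or falls ill during the 12 weeks has no Pilates exposure to which the event could be attributed, so it cannot be counted. A control count of zero would come from the definition and would not be an observation.
2. In Groups A and B an event is kept or dropped according to a judgement about its cause. The plan does not say who makes that judgement, by what criteria, or with what knowledge of the allocation. A low count could reflect few events or strict attribution, and the record would not show which.

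At stake is the value of having a control arm for safety. The trial compares two training volumes in older adults, and a reader will want to see the injuries and illnesses in each Pilates group beside those in people who carried on as usual. The plan as written cannot supply that comparison, even descriptively.

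**Working it through.** **Inputs.** 15 per group, three groups and 20% losses, giving 57 (Statistical analysis plan; Participants). The documents give no event rate and no attribution rate. Those used below are assumptions, shown as ranges.

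**Step 1: the plan's own figure.** 15 / (1 − 0.20) = 18.75, rounded up to 19 per group, and 3 × 19 = 57. This matches the plan, so 19 per group is used below. The point itself does not depend on this number.

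**Step 2: the control count follows from the text.** An event counts if it is attributable to Pilates, and the control group does no Pilates. The recorded control count is therefore 0 at any true event rate. No assumption is needed.

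**Step 3: what the rule would leave out in the control group.** Let r be the assumed 12-week risk of at least one injury or medical event of any cause. The expected number of control participants affected is 19r, and the chance that at least one is affected is 1 − (1 − r)^19.

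| r (assumed) | Expected affected of 19 | Chance of at least one | Recorded under the rule |
|---|---|---|---|
| 5% | 0.95 | 62% | 0 |
| 10% | 1.9 | 86% | 0 |
| 20% | 3.8 | 98.6% | 0 |
| 30% | 5.7 | 99.9% | 0 |

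For scale, a true observation of 0 out of 19 has an exact two-sided 95% upper limit of 1 − 0.025^(1/19) = 17.6%. Even a real zero would say little, and a zero by definition says nothing about the rate.

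**Step 4: how far attribution moves the Pilates counts.** Let q be the assumed proportion of events judged attributable. The expected recorded count per Pilates group is 19 × r × q. At r = 10%:

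- q = 25%: 19 × 0.10 × 0.25 = 0.48
- q = 50%: 19 × 0.10 × 0.50 = 0.95
- q = 75%: 19 × 0.10 × 0.75 = 1.43

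The same 1.9 affected participants give a recorded count that differs threefold, depending only on the judgement.

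**Step 5: whether another part of the plan fills the gap.** The assessments before and after the intervention list no adverse events. Reasons for absence are recorded for Pilates sessions, so they may pick up some unrelated illness or injury in Groups A and B but none in the control group. Neither supplies a background rate.

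**Step 6: what complete recording could show.** At 19 per group, the power of Fisher's exact test (two-sided 0.05) is about 7% for 10% against 20%, 22% for 10% against 30%, and 18% for 20% against 40% (all assumed rates). An observed 2 of 19 has an exact 95% interval of 1.3% to 33%. The gain is in description, not in testing.

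**The case against.** The strongest reply is that the trial does not ask a comparative safety question. Safety is one of four feasibility items, and its neighbours, adherence and participant experience, also concern the Pilates programme itself. It is absent from the aim, the outcomes and the sample size basis, and no between-group safety test is named. Listing intervention-related events is a thin but coherent feasibility measure. This stands: no planned analysis becomes invalid, and the point is therefore an improvement, not a flaw in the main design.

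Three further points limit it.

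- **Blinding of attribution.** A reader might infer that the plan uses an unblinded attribution step. The documents do not say so, because they name no assessor. Judging an event attributable to Pilates does require knowing that the person did Pilates, but the assessor could still be blind to A versus B. The supportable statement is that assessor, criteria and blinding are unspecified.
- **Interpretability.** A reader might infer that the Pilates counts cannot be interpreted at all. That goes too far. The same definition applies to A and B, so related events can be described for one against the other. What is missing is the rate under usual activity.
- **Grammar.** The attribution phrase could be read as qualifying medical events only, leaving injuries unrestricted. The natural reading covers both. On the narrower one, medical events in the control group would still be uncountable, and the wording would still need clarifying.

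**Conclusion.** The point holds as a cheap improvement. The zero control count rests on the natural reading of one sentence and on the absence of any other adverse-event text; it needs no assumed rate. Its size does: at an assumed all-cause risk of 5% to 30% over 12 weeks, about 1 to 6 of 19 controls would have an event that the rule leaves out, and the Pilates counts would scale directly with the unstated attribution judgement.

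A reader might also infer that better recording would let the trial establish whether the higher volume adds injuries. It would not: the power and interval figures above show that 19 per group is too few. The figures illustrate what goes unrecorded; they do not measure a bias in any planned result.

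**What to change.** Reword the safety item along these lines:

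- Record every injury and medical event in all three groups over the 12 weeks, using the same question at the same times.
- Put the question also to participants who withdraw or miss the final visit, for example by telephone. The final assessment alone is not enough, because the plan expects 20% losses and excludes people who miss evaluations. Someone lost because of an event would otherwise go unrecorded.
- Ask it after the blinded tests, or have staff other than the blinded evaluators ask it, so that the answers do not reveal the allocation.
- Record relatedness to Pilates as a separate field, and state who judges it, by what criteria, and whether that person is blinded.
- Report all-cause and related events by group, as participants affected with exact confidence intervals, descriptively.

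The cost is a wording change, a few extra questions and some follow-up calls. The listing will contain unrelated events, and the intervals will be too wide for a firm between-group safety conclusion. The efficacy analyses and the sample size need no change.

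### Sex is neither a stratification factor nor a term in the group comparison, and baseline values are not used either, so the force and lung comparisons lose precision and are open to chance imbalance

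*Combined protocol and SAP*

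**What the plan says.** The Abstract states that "it will be a randomized clinical trial with elderly of both sexes". The Participants section takes, "considering the possibility of 20 % of sample losses, the first 57 eligible participants" who meet the criteria, with no quota by sex.

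Under Evaluation procedures, the account of allocation is "Subjects will be randomized into three groups. The randomization process will be done at random.org". Envelopes are named as the means of concealment. No ratio, blocking, stratification or minimisation is described.

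Under Muscle Strength, "E-lastic® will measure maximal isometric voluntary contraction of the knee flexor and extensor muscles" and of the hip muscles, where "a load cell is used to provide an electrical signal proportional to the force that deforms the equipment"; the highest of three values is kept. Grip is also a force. The 30-second chair stand is a count. MIP and MEP are in cmH2O, and FVC and FEV1 in litres. Grip is to be set against reference values, and the respiratory pressures and spirometry against predicted values, but the Statistical analysis plan does not make any such scaled value the variable compared between groups.

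That section compares the three groups by one-way ANOVA or Kruskal-Wallis with Bonferroni correction and names no covariate. Sex is collected to describe the sample. Every outcome is measured before and after the intervention, but the baseline value enters only the within-group paired tests.

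**The concern.** Maximal force, respiratory pressures and lung volumes are outcomes on which men and women can be expected to differ. With small groups, an uneven split of men between two groups moves their mean difference for a reason unrelated to the Pilates programme. Even when the split is even, the difference between the sexes stays in the error term and makes every comparison less precise.

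Muscle strength is one of the three domains on which the trial is sized. The hypothesis in the Introduction is that the higher-volume group improves more than the lower-volume group. That is a contrast between two active programmes, whereas the sizing used intervention versus control, so the difference of main interest may be smaller than the one planned for. Neither the allocation nor the analysis, as described, deals with sex.

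**Working it through.** **Inputs from the documents.** 15 per group, 80% power, alpha 0.05; three groups; 20% losses; 57 enrolled. **Assumed, because the documents give no figure:** equal groups of 19; 15% to 35% men, taken as 9, 14 or 20 men of 57; a male-female gap D of 1 to 2 within-sex SDs.

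**1. The plan's own total.** 3 × 15 = 45; 45 / (1 − 0.20) = 56.25, rounded up to 57, or 19 per group. The 57 reproduces. The 15 per group cannot be rebuilt because no effect size is printed: "A sample size was calculated using the effect size identified in the comparison of the results concerning the post-intervention moment". Solving backwards (t test, two-sided 0.05, 80% power), 15 per group detects 1.06 SD.

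**2. Precision.** Total SD / within-sex SD = √(1 + p(1 − p)D²), where p is the male share.

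| | p = 0.15 | p = 0.35 |
|---|---|---|
| D = 1 | √1.1275 = 1.06 | √1.2275 = 1.11 |
| D = 2 | √1.51 = 1.23 | √1.91 = 1.38 |

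If the 1.06 is in total SDs, power at 15 per group by the normal approximation is Φ(1.06 × √7.5 − 1.96) = 0.83. Removing the sex variance multiplies 1.06 by the ratio above, and power becomes 0.87 (ratio 1.06) to 0.98 (ratio 1.38).

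**3. Chance imbalance.** With men falling at random into 3 × 19, the number of men per group is hypergeometric.

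| Men of 57 | One named contrast, gap ≥ 3 | gap ≥ 4 | Any of three pairs, gap ≥ 3 | gap ≥ 4 |
|---|---|---|---|---|
| 9 | 27% | 12% | 47% | 26% |
| 14 | 35% | 19% | 64% | 40% |
| 20 | 40% | 24% | 69% | 47% |

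The median gap for a named contrast is 2 men.

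**4. Size of the shift.** A 4-man gap is 4/19 = 21 percentage points and shifts the contrast by D × 4/19, which is 0.21 to 0.42 within-sex SD. The planned ANOVA works on the total SD, so divide by the ratios in step 2. The lowest value is 0.211 / 1.108 = 0.19 and the highest is 0.421 / 1.229 = 0.34. For scale, the standard error of a two-group contrast at 19 per group is √(2/19) = 0.32 total SD.

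**5. Type I error.** Simulated one-way ANOVA with no treatment effect, 19 per group, 20% to 50% men and D of 1 to 2:
- overall: 0.048 to 0.052;
- when some pair of groups differs by at least 20 points in percent male: 6.5% to 11%;
- when some pair differs by at least 30 points: 10% to 23%.

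Allocations without such an imbalance fall below 5%, which is why the overall rate is preserved.

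**The case against.** The strongest case against is that unstratified randomisation is a legitimate design. It gives no bias on average, and step 5 shows that the test keeps its level. That stands. A reader might infer that the planned strength comparison is biased, or that it compares sexes rather than programmes; the documents do not support this, because the harm depends on an imbalance that may not occur.

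A reader might also take the any-pair figures (up to 69% for 3 men) as the risk to the main hypothesis. For GA versus GB the relevant figures are 27% to 40% for 3 men and 12% to 24% for 4. Over most of the assumed range, the shift from a 4-man gap is smaller than one standard error of the contrast.

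Three further limits stand.
- The absence of stratification is inferred from silence; if a scheme exists, one sentence settles that part.
- The Statistical analysis plan does not say whether the between-group test takes post-intervention values or changes. The sizing basis points to post-intervention values. If changes were analysed, the sex difference in level would largely drop out.
- The chair stand is not a force, and percent-predicted values, if analysed, would ease the problem for the lung measures.

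The paired tests do not answer the point. They remove each person's level, but within a group, and so make no comparison between programmes.

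**Conclusion.** The point holds as a matter of precision and of protection against chance imbalance, not as an error of validity. It applies to E-lastic force, grip, MIP/MEP and FVC/FEV1 in raw units, and not to the chair-stand count. Nothing here shows a problem for balance or flexibility, the other two domains used for sizing.

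The certain part is that between-sex variance stays in the error term. The contingent part is a shift of roughly 0.2 to 0.3 total SD should a 4-man gap arise in the contrast of interest. Both sizes rest on the assumed male share and sex gap and would shrink if either were smaller. Since sex and baseline values are collected anyway, the plan should use them.

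**What to change.** **Main change, in the Statistical analysis plan.** Replace the between-group one-way ANOVA with a prespecified ANCOVA of the post-intervention value on group, the baseline value of the same outcome and sex, with Bonferroni-adjusted pairwise contrasts. Adjusting for baseline matters as much as adjusting for sex, because a person's own starting force or lung volume already carries much of the sex difference. State also what replaces the Kruskal-Wallis branch when residuals are clearly non-normal, for example the same model on ranks. The cost is two degrees of freedom (with 57 analysed, residual degrees of freedom go from 54 to 52). No new data are needed and the total stays at 57.

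**Optional, low-cost change, in Evaluation procedures.** Generate separate random.org lists for men and women in permuted 1:1:1 blocks of 3 and 6, and keep two series of opaque sealed envelopes. An unfinished block of 6 can leave a gap of 2 men, so imbalance at randomisation is limited to about 2; fixed blocks of 3 would limit it to 1 but make the sequence easier to guess. The costs are a second envelope series, some predictability of the last allocations in a block in both strata, and total group sizes that may differ by up to 2 + 2 = 4 if both lists end mid-block. Stratification protects balance at randomisation only. Losses, and the exclusion of participants who complete less than 80% of the intervention, can undo it, which is a further reason to put the adjustment in the analysis first.
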